7.3.1. Bleeding

Bleeding will be classified according to the 18TH definitions (see section 17.3). Bleeding events will also be classified according to BARC (14) and TIMI (21, 22) classifications for descriptive purposes only.

7.3.2. Components of MEE

The following endpoint definitions will be applied:

CV death, defined as cardiac or vascular death according to Academic Research Consortium (ARC) (23) ..

- Thromboembolic death (thromboembolic death considered to be thromboembolic in origin (including thromboembolic stroke, pulmonary embolism, any other systemic embolism), defined as CV death excluding fatal bleeding defined as BARC sub-category 5 (14).
- A stroke is defined as an abrupt onset, over minutes to hours, of a focal neurological deficit in the distribution of a single brain artery that is not due to an identifiable nonvascular cause (i.e., brain tumor or trauma), and that either lasts at least 24 hours or results in death within 24 hours of onset (13). Stroke will be sub-divided into ischemic, hemorrhagic or indeterminate. Stroke is categorized in disabling and non-disabling stroke using the mRS score.

TIA is defined as an abrupt onset, over minutes to hours, of a focal neurological deficit in the distribution of a single brain artery, that lasts less than 24 hours and is not due to an identifiable non-vascular cause (i.e., brain tumor or trauma) and does not satisfy the stroke definition above. (13)

An SEE is defined as an arterial embolism resulting in clinical ischemia, excluding the central nervous system (CNS), coronary and pulmonary arterial circulation (13).

Spontaneous MI according to Universal MI definition (24) and periprocedural MI according to the SCA! MI definition (25)

Stent thrombosis according to ARC (23)

7.3.3. Other

Intracranial hemorrhage is a sub-category of ISTH major in a specified critical organ, to be determined by the CEC.

8. PHARMACOKINETIC ASSESSMENTS .

8.1. Pharmacokinetic (PK) Variable(s)

Not applicable.

8.2. Non-genetic biomarkers and Exploratory Variable(s)

Not-applicable (please-refer to-section- n 2)

9. SAFETY ASSESSMENTS

Safety assessments that are components of the study endpoint assessments (e.g. bleeding endpoints) are detailed in Section 7.3 and must be collected in the AE/Outcome eCRF page,

9.1. Adverse Events (AEs)

9.1.1. Definitions

9.1.1.1. Adverse Event (AE)

Any untoward medical occurrence in a subject administered a pharmaceutical product and which does not necessarily have a causal relationship with this treatment. An AE can therefore be any unfavourable and unintended sign (including an abnormal laboratory finding for example), symptom, or disease temporally associated with the use of a medicinal (investigational) product, whether or not considered related to the medicinal (investigational) product.

9.1.1.2. Unexpected Adverse Event

An unexpected AE (uAE) is an AE, the nature or severity of which is not consistent with the reference safety information of any of the study medication. The designation of expected or unexpected must be decided from the perspective of previously described AEs, not on the basis of what might be anticipated from pharmacological properties of a medicinal product. The investigator can provide his judgment on the expectedness/unexpectedness of a reported AE to the sponsor and this will be taken into account for the sponsor's judgment of expectedness. However, the final determination of expectedness is the responsibility of DSE and not the investigator.

9.1.1.3. Expected Adverse Event

An expected AE is an event which is described in the reference safety information of the study drug in nature, severity or incidence.

9.1.1.4. Serious Adverse Event (SAE)

An SAE or reaction is any untoward medical occurrence that at any dose:

- results in death.
- is life-threatening.
The term "life-threatening" in the definition of "serious" refers to an event in which the subject was at risk of death at the time of the event; it does not refer to an event which hypothetically might have caused death if it were more severe.
- requires inpatient hospitalisation or prolongation of existing hospitalisation.
- results in persistent or significant disability/incapacity.
- is a congenital anomaly/birth defect.

OR

- is any other medically important condition (see below).

Note: Medical and scientific judgement should be exercised in deciding whether expedited reporting is appropriate in other situations, such as important medical events that may not be immediately life-threatening or result in death or hospitalisation, but may jeopardise the subject or may require intervention to prevent one of the other outcomes listed in the definition above. These should also usually be considered serious. Examples include allergic bronchospasm, convulsions, and blood dyscrasias or development of drug dependency or drug abuse.

Note:

- A procedure is not an AE or SAE, but the reason for the procedure may be an AE or SAE.
- Treatment requiring hospitalizations for pre-existing conditions which do not worsen **in** severity are not SAEs.

9.2. Classification for AE assessment

9.2.1. Severity of Adverse Events

The severity of an AE is graded as follows:

Mild: Discomfort noted, but no disruption of normal daily activity.

Moderate: Discomfort sufficient to reduce or affect normal daily activity.

Severe: Inability to work or perform normal daily activity.

9.2.2. Relationship of Adverse Events

The Investigator should assess causal relationship between an adverse event and the assigned anticoagulant-based regimen (i.e., edoxaban-based or VKA-based) on the basis of his/her clinical judgment and the following definitions. The causality assessment should be made based on the available information and can be updated as new information becomes available.

- **1 = Related:**
The AE follows a reasonable temporal sequence from the assigned anticoagulant-based regimen administration, and cannot be reasonably explained by the subject's clinical state or other factors (e.g., disease under study, concurrent diseases, and concomitant medications).
The AE follows a reasonable temporal sequence from the assigned anticoagulant-based regimen administration, and is a known reaction to any of the study medications (i.e. the components of each

study regimen) under study or its chemical group, or is predicted by known pharmacology.

- 2 = Not Related:
The AE does not follow a reasonable sequence from the assigned anticoagulant-based regimen administration, or can be reasonably explained by the subject's clinical state or other factors (e.g., disease under study; concurrent diseases and concomitant medications).

9.2.3. Action Taken Regarding the Assigned Antithrombotic Regimen

For each drug of each antithrombotic regimen (either, edoxaban and clopidogrel in the edoxaban-based regimen or VKA, P2Y₁₂ inhibitor and ASA in the VKA-based regimen), the action taken after an AE must be recorded in the eCRF as delineated below:

- 1 = Dose Not Changed: No change in dosage was made.
- 2 = Drug Withdrawn: Permanently stopped.
- 3 = Dose Reduced: The dosage was reduced.
- 4 = Drug Interrupted: Temporarily stopped.
- 5 = Dose Increased: The dosage was increased.

9.2.4. Other Action Taken for Event

- 1 = None: No treatment was required.
- 2 = Concomitant medication required: Prescription and/or over-the-counter medication were required to treat the adverse event.
- 3 = Concomitant medication permanently discontinued: Prescription and/or over-the-counter medication other than the assigned anticoagulant-based regimen was permanently discontinued due to the adverse event.
- 4 = Concomitant medication temporarily interrupted: Prescription and/or over-the-counter medication other than the assigned anticoagulant-based regimen was temporarily interrupted due to the adverse event.
- 5 = Other.

9.2.5. AE Outcome

- 1 = Recovered/Resolved: The subject fully recovered from the adverse event with no residual effect observed.
- 2 = Recovered/Resolved with Sequelae: The residual effects of the adverse event are still present and observable. Include sequelae/residual effects.

3 = Not Recovered/Not Resolved: The adverse event itself is still present and observable.

4 = Fatal

5 = Unknown

The Investigator should follow subjects with AEs until the event has resolved or the condition has stabilized. In case of unresolved adverse events including significant abnormal laboratory values at the end of study assessment, these events will be followed up until resolution or until they become clinically not relevant.

9.3. AEs of Special Interest

9.3.1. Combined Elevations of Aminotransferases and Bilirubin

There was no clinically concerning signal of drug-induced liver injury associated with edoxaban based on the extensive global phase 3 experience involving over 34,100 edoxaban subject-years exposure (with median drug exposure of ~2.5 years among ~14,000 edoxaban subjects). However, there will be ongoing monitoring of hepatic events, including combined elevations of aminotransferases and bilirubin (ALT or AST > 3 x ULN with simultaneous TBL > 2 x ULN), particularly those without evidence of cholestasis (ALP 2: 2xULN is considered evidence of possible cholestasis) and without alternative etiology for hepatocellular damage.

Combined elevations of aminotransferases and bilirubin, either serious or non-serious and whether or not causally related, should always be reported to the Sponsor as soon as possible following the procedures outlined in Section 9.5 for SAE reporting.

In cases of liver laboratory abnormalities, or evidence of liver dysfunction, it is important to ensure that the etiology of liver injury is identified and study subjects are monitored until the liver laboratory assessments return to normal.

9.3.2. Reporting of Pregnancy/Exposure in Utero

The sponsor or designee must be notified of any subject that becomes pregnant while participating in a clinical study. All pregnancies must be followed to conclusion to determine their outcome. This information is important for both drug safety and public health concerns. It is the responsibility of the Investigator, or designee, to report any pregnancy in a subject, which occurs during the study,.

If any study subject or their partner becomes or is found to be pregnant while receiving, or within 30 days of discontinuing the investigational product, the Investigator should contact the Medical Monitor to discuss subject management and receive further information. Notification of the pregnancy, should be submitted in the eCRF (AEs of special interest) within 24 hours and reported using Exposure in Utero Reporting form (paper for:n).

If it is the partner, rather than the subject, who is found to be pregnant, the Exposure in Utero Reporting Form should be completed with the subjects' identification number, and year of birth. Details regarding the partner should be entered in the narrative section of the Exposure in Utero Reporting form if a consent of the trial subject's partner has been obtained by the Investigator.

If the pregnancy is to be terminated, the anticipated date of termination should be reported. If the pregnancy ends for any reason before the anticipated date, the Investigator should notify the Sponsor. If the outcome of the pregnancy meets the **criteria for immediate classification as a SAE (i.e. post-partum complications, spontaneous abortion, stillbirth, neonatal death, or congenital anomaly, including that in an aborted fetus)**, the Investigator should follow the procedures for reporting an SAE. At the completion of the pregnancy, the Investigator will document the outcome of the pregnancy in a follow-up Exposure in Utero Reporting Form.

9.4. Timing of Adverse Event Reporting

All AEs must be recorded and reported from the stated starting point of the clinical trial (immediately after signing IC) including AEs taking place during the administration of other drugs. Even if the subject has not yet received the investigational study regimens, untoward medical occurrences have to be treated as AEs.

The period of AE reporting is defined as follows:

AEs that occur within 30 days after the last dose of the assigned study anticoagulant-based regimen which are reported to the Investigator (regardless of the date of a follow-up visit) must be recorded in the eCRF.

9.5. Reporting SAEs/AEs

9.5.1. Documentation

To effectively evaluate the safety profile of the anticoagulant-based regimens, this study will report all (S)AEs occurring after the subject signs the IC and up to 30 days after the last dose of the assigned anticoagulant-based regimen, whether observed by the Investigator or reported by the subject. All AEs will be recorded on the AB/Outcome eCRF page and include:

- Any components of the study endpoint assessments (see Section 7);
- AE that meet seriousness criteria (see Section 9.2.1);
- AE that result in interruption or discontinuation of the assigned anticoagulant-based regimen;
- AE that meet the criteria for AE of special interest (see Section 9.3);
- Any other AE.

All laboratory results and vital signs should be evaluated by the Investigator regarding clinical significance. Isolated abnormal laboratory results or vital sign findings that are not part of a diagnosis should be reported as AEs or SAEs.

Medical conditions (including laboratory values/vital signs that are out of range) that were diagnosed or known to exist prior to IC will be recorded as part of medical history.

All SAEs are to be reported according to the procedures in Section 9.5.2 below.

Always report the diagnosis as the AE or SAE term. When a diagnosis is unavailable, report the primary sign or symptom as the AE or SAE term with

~~additional details included in the narrative until the diagnosis becomes available.~~

If the signs and symptoms are distinct and do not suggest a common diagnosis, report them as individual entries of AE or SAE. For events that are serious due to hospitalization, the reason for hospitalization must be reported as the serious adverse event (diagnosis or symptom requiring hospitalization).

AEs may be directly observed, reported spontaneously by the subject or by questioning the subject at each study visit. Subjects should be questioned in a general way, without asking about the occurrence of any specific symptoms. The Investigator must assess all AEs to determine seriousness, severity, and causality, in accordance with the definitions in Section: 9.2. The Investigator's assessment must be clearly documented in the site's source documentation with the Investigator's signature.

In case of an occurrence of an (S)AE, the Investigator applies the following rules:

- Ensure appropriate medical treatment and decide whether to discontinue or interrupt any of the study medications.
- Complete the initial AE/Outcome eCRF page upon event awareness.
- Record the event, its management, and outcome in the eCRF page.
- For SAEs, report in the eCRF **within 24 hours** of receiving knowledge of the occurrence. In the event that all the required information is not available, the information which is available is to be sent without delay (within 24 hours), and the outstanding data relayed as soon as available thereafter. Answer any queries related to the reported SAE as soon as possible.
- For AEs of special interest, report **within 24 hours** of receiving knowledge of the occurrence as defined for SAEs above.
- For AEs, obtain all data required incl. any information which, is only available after considerable delay (i.e. hospital reports, outcomes, resolution end dates), **as soon as available**.
- Components of the study endpoint assessments which result in death must be reported as SAEs **within 24 hours** of the Investigator's awareness.

9.5.2. Notifying Regulatory Authorities, Investigators and IRB/IEC,

Detailed SAE processing, distribution and reporting will be laid out in sponsor's SAE Flow Plan.

Sponsor and/or ARO/CRO will inform Investigators, IRBs (Institutional Review Board)/IECs (Independent Ethics Committees), and regulatory authorities of any Suspected Unexpected Serious Adverse Event Reactions (SUSARs) occurring in the study or other sponsor studies of the investigation product (excluding waived study endpoint events per Section 6.6), as appropriate per local reporting requirements.

In the European Union countries, it is the Sponsor's responsibility to report SUSARs to regulatory authorities and IECs.

Study endpoints are clinically anticipated events in AF subjects receiving antithrombotic therapy and will be periodically reviewed by the DSMB in a blinded manner to ensure prompt identification of any clinically concerning safety issues.

9.6. Clinical Laboratory Evaluations

Refer to the Laboratory Manual for detailed instructions of sample collection, storage, and shipment. The results will be reviewed and compared to the central laboratory's normal ranges. The visits at which these samples will be collected are shown in the schedule of assessments (Appendix 17.9).

The following safety laboratory evaluations are performed in individual blood samples.

- Liver Function Panel
 - o Total bilirubin (conjugated/unconjugated, performed when total serum bilirubin \geq 2 mg/dL)
 - o Alanine transaminase (ALT)
 - o Aspartate transaminase (AST)
 - o Alkaline phosphatase (ALP)
- Serum Chemistry Panel
 - o Creatinine
- Hematology Panel
 - o White blood cell (WBC) count with differential if elevated
 - o Hemoglobin
 - o Platelet count
- INR
- Urine Sampling (only at baseline and follow up for pregnancy testing). Pregnancy tests will be provided for female patients with childbearing potential (related to women who are pre-menopausal) to be performed at home in case of visits by phone.

All other assessment are collected from local laboratory"results for tests done as part of routine care. Local laboratory assessments are used for parameters required

to verify eligibility and for parameters that require monitoring according to local routine.

9.7. Vital Signs

The following parameters are recorded for vital signs:

- Blood pressure (BP), sitting diastolic and systolic BP
 - Weight
 - Height (only at baseline)
-

9.8. Electrocardiograms

Twelve-lead ECG are collected according to the schedule of assessments (section 17.9). Investigational sites will utilize local ECG equipment and record pertinent information in the eCRF while preserving all recorded ECG tracings as subject source documentation.

9.9. Physical Findings

The Investigator or a licensed team member performs targeted physical examination according to the schedule of assessments. This physical examination consists of assessment of each of the relevant (including but not limited to cardiac, neurologic, pulmonary, GI) major body systems. In order to be able to detect any renal impairment, the Creatine Clearance will be calculated. In addition, All information needed for the calculation will be collected in the eCRF. Any clinically significant findings must be recorded in the eCRF under medical history at baseline and under AB/Outcome until the subject's final contact.

10. OTHER ASSESSMENTS

10.1. Coronary angiograms

The pre- and post-index PCI coronary angiograms are recorded according to the standard of care.

10.1.1. Hospitalisations,

In addition to the standard SAE data collected for hospitalisation as described in Section 9.1.1.4, additional data will be collected for hospitalisations that are reported for one of the following reasons:

- Bleeding
- Stroke
- SEE
- Myocardial infarction
- Stent thrombosis

Data on length of hospital stay (admission and discharge dates), admission unit (e.g. ICU), admission diagnosis and discharge status will be collected for any of the above hospitalisations.

In addition, data on non-protocol driven outpatient physician or nurse visits, emergency room visits, or the use of long-term care, rehabilitation, or skilled nursing facilities related to bleeding, stroke, SEE, myocardial infarction, or stent thrombosis will be collected throughout the study.

11. STATISTICAL METHODS

11.1. Analysis Sets

11.1.1. Intention-to-treat analysis set

The Intention-to-treat Set (ITT) consists of all randomized subjects irrespective whether they received a single dose of the randomized study regimen or not.

Analyses will be based on the randomized treatment regimen even if a subject inadvertently receives the incorrect drug(s) or dosage or has his/her edoxaban dose adjusted (decreased/increased) one or more times during the study. The reference date for consideration of endpoints is the date and time of randomization.

11.1.2. Modified Intention-to-treat analysis set

The modified Intention-to-Treat Analysis Set (mITT) consists of all randomized subjects who received at least one dose of study edoxaban or study VKA according to IXRS assignment.

Analyses will be based on the randomized treatment regimen even if a subject inadvertently receives the incorrect drug(s) or dosage or has his/her edoxaban dose adjusted (decreased/ increased) one or more times during the study. The reference date for consideration of endpoints is the date and time of first intake of study edoxaban or study- VKA.

11.1.3. Per Protocol analysis set

The Per Protocol Analysis Set (PP) consists of all randomized subjects who received at least one dose of the study regimen according to IXRS assignment and do not have any of the following major protocol violations:

- A major violation of the inclusion criteria
 - o No stent placement
 - o No successful PCI (see section (definition))
 - o Planned further (staged) PCI
 - o No AF
 - o Known contraindication for OAC
- An unequivocal violation of the exclusion criteria

The list of major violations will be finalized before data base lock. The list and the exclusions will be confirmed in a blinded way, i.e. without knowledge of the randomized study regimen and of the clinical outcomes.

Analyses will be based on the randomized treatment regimen, even if a subject inadvertently receives the incorrect drug(s) or dosage or has his/her edoxaban dosage adjusted (decreased/ increased) one or more times during the study. The reference date for consideration of endpoints is the date and time of first intake of study edoxaban or study VKA.

11.1.4. Safety analysis set

The Safety (SAF) Analysis Set consists of all randomized subjects who received at least one dose of the study edoxaban or study VKA according to IXRS assignment.

Analyses will be based on the randomized treatment regimen, even if the subject's edoxaban dosage is adjusted after randomization, unless a subject inadvertently receives the incorrect drug(s) or dosage during the entire study, in which case the subject will be grouped according to the treatment actually received. The reference date for consideration of endpoints is the date of first study medication intake.

Note: This SAF analysis set is identical to the mITT analysis set and will be used for the safety parameters (e.g. adverse events, vital signs, laboratory parameters, etc.) as described under section 9.

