- The *Intention-to-treat (ITT) analysis set* consists of all randomized subjects irrespective whether they received a single dose of the randomized study regimen or not.
- The *Modified Intention-to-treat (mITT) analysis set* consists of all randomized subjects who received at least one dose of study edoxaban or study VKA according to IXRS assignment.
- The *Per Protocol (PP) analysis set* consists of all randomized subjects who received at least one dose of the study regimen according to IXRS assignment and do not have any of the following major protocol violations:
 - A major violation of the inclusion criteria
 - An unequivocal violation of the exclusion criteria, (for more details, see Section 11.1.3)
- The *Safety (SAF) analysis set* consists of all randomized subjects who received at least one dose of the study edoxaban or study VKA according to IXRS assignment.

Definition of terms:

'Overall Study Period': This period is defined as the time from the reference date (date and time of randomization or date and time of first study edoxabari or study VKA intake) to Day 365.

'Overall Study Period + 30 days': This period is defined as the time from the reference data (date and time of randomization or date and time of first study edoxaban or study VKA intake) to Day 395.

'Initial dose to Final Dose + 30 days': This period is defined as the time-period between the date and time of initial dose of study edoxaban or study VKA and the date of final dose of study edoxaban or study VKA plus 30 days, including study regimen interruptions.

The main analysis of all adjudicated primary and secondary exploratory endpoints will be based on ITT analysis set and taking the first adjudicated event during the 'overall study period' into account.

For each of the primary and secondary exploratory endpoints, appropriate summary statistics (e.g. event rate) including 95% CI will be provided.

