6.1.1. Pre-screening

The following activities and/or assessments are performed at/during study screening:

- A re-check that the subject meets all of the inclusion criteria and none of the exclusion criteria (see Section 4.1);
- Last local laboratory test results, done post-index PCI:
 - Estimated CrCL (according to the Cockcroft-Gault formula, see Appendix 17.6),
 - Hemoglobin (Hgb),
 - platelet count, and
 - WBC (with differential if elevated).
- Checking the last available INR value (pre-randomization), done within the past 24 hours; INR must be ≤ 2.5

6.1.2. Baseline/ Randomization - Day 1

Prior to randomization:

- After contacting the IXRS, the Investigator provides the following information to the IXRS:

- Confirmation written IC has been obtained;
- Confirmation subject fulfills all inclusion and none of the exclusion criteria;

Demography (age, body weight and gender);

Clinical presentation (ACS or stable CAD);

- Last value of estimated Creatinine clearance (CrCL);
- INR value prior to randomization;
Usage of a P-gp inhibitor that requires an edoxaban dose reduction (according to local edoxaban SmPC or IB as applicable);
- Documentation of P2Y12 inhibitor other than clopidogrel and pre-declaration of the P2Y12 inhibitor to be prescribed (i.e., prasugrel, or ticagrelor);
- Pre-declaration of the intended duration of ASA (100 mg once-daily) therapy (I - 12 months), if randomized to the VKA-based regimen; Please consider subject's medical history including components of the CHA2DS2-VASc score, HAS-BLED score (Appendix 17.5);

Randomization:

- If the reported INR \leq 2.5 and reported CrCL \geq 15 mL/min, the IXRS accepts subject's eligibility and assigns the following:
 - o subject identification number
 - o the randomized treatment regimen
 - o presence of edoxaban dose reduction requirement
 - o kit numbers of the medications to be used
- The day of randomization will be Day 1.
- Urine sampling for pregnancy testing for women of childbearing potential (related to women who are pre-menopausal) (local laboratory)

Immediately after randomization:

The following activities are done after randomization and recorded in eCRF:

- Collection of blood samples for the following central laboratory tests:
 - Safety samples for: liver function, serum chemistry, hematology and INR

The samples are processed and sent to the central laboratory (Section 9.6 and 8.2, respectively).

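### The Safety set's entry rule excludes a subject who took only the other arm's anticoagulant, so the as-treated clause cannot work for the case it most naturally covers

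*Combined protocol and SAP*

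**What the plan says.** Section 11.1.4 sets the entry condition for SAF: a randomized subject must have "received at least one dose of the study edoxaban or study VKA according to IXRS assignment". The synopsis, under Statistical Analyses, uses the same condition: "all randomized subjects who received at least one dose of the study edoxaban or study VKA according to IXRS assignment".

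The next paragraph of 11.1.4 groups subjects by randomized regimen, with one exception: "unless a subject inadvertently receives the incorrect drug(s) or dosage during the entire study". The clause then states how such a subject is handled: "in which case the subject will be grouped according to the treatment actually received". A note closes the section: "This SAF analysis set is identical to the mITT analysis set".

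Section 11.1.2 gives mITT the same entry condition, "received at least one dose of study edoxaban or study VKA according to IXRS assignment", but no as-treated exception: "Analyses will be based on the randomized treatment regimen even if a subject inadvertently receives the incorrect drug(s) or dosage".

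SAF is the named set for the adverse event, laboratory and vital-sign summaries (Sections 11.5.1 to 11.5.3). Section 11.5.1 also defines treatment-emergent events by the first and last dose of the assigned regimen. The main analyses of the primary and secondary endpoints use ITT (Section 11.2).

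**The concern.** A safety population normally holds everyone who was exposed, tabulated under what they took. The exception in 11.1.4 shows that the authors want this for a subject who was on the wrong drug throughout. The entry condition works against that aim, because it asks for a dose of the assigned anticoagulant before any grouping rule applies.

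A programmer who follows the entry condition drops such a subject from the SAF summaries. One who follows the grouping clause keeps a subject whom the definition excludes. The text should settle this before data are available, particularly in an open-label trial whose primary question is bleeding. The protocol does foresee such errors: Section 6.4 requires follow-up to 12 months even after a subject has been given the wrong drug or dosage.

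**Working it through.** The plan gives no figure on this point, so the check is one of set logic.

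**Inputs**

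- A = at least one dose of the assigned study anticoagulant. This is the SAF entry condition in 11.1.4 and the synopsis, reading IXRS assignment as the randomized anticoagulant.
- B = the wrong anticoagulant during the entire study. This is the trigger of the exception in 11.1.4, for the anticoagulant.

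**Step 1.** B means zero doses of the assigned anticoagulant, so B implies not-A. SAF requires A. SAF and B therefore have no subject in common.

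**Step 2.** Conversely, a subject in SAF has had at least one assigned dose. The anticoagulant was then not wrong for the entire study, and the trigger is not met.

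**Step 3.** The possible situations under the text as written:

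| Subject took | In SAF? | Exception triggered? | Result |
|---|---|---|---|
| Assigned anticoagulant, with or without some doses of the other | Yes | No | Analysed as randomized |
| Only the other arm's anticoagulant | No | Yes | Excluded; clause has no effect |
| No anticoagulant | No | Not relevant | Excluded, as intended |
| Assigned anticoagulant, wrong dosage throughout | Depends on whether the assignment includes the dose | Yes, if in SAF | Same regimen, so the arm does not change |
| Assigned anticoagulant, wrong antiplatelet drug throughout | Yes | Arguably | Combination need not match either arm; no clear regrouping |

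In no row does the clause move a subject to the other anticoagulant arm.

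**Step 4.** The note in 11.1.4 does not rescue the second row. mITT has the same entry condition, so equating the two sets repeats the exclusion. No other section restores these subjects to the SAF summaries.

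**Step 5, size.** The documents give no rate of wrong-anticoagulant allocation. With N = 1500 planned and an assumed proportion p who took only the other anticoagulant, the number excluded is 1500 × p:

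- p = 0: 0 subjects
- p = 0.2%: 1500 × 0.002 = 3 subjects
- p = 1%: 1500 × 0.01 = 15 subjects

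**The case against.** **Another reading of the entry condition.** The IXRS assigns not only the regimen but also the "kit numbers of the medications to be used" (Section 6.1.2), and all VKA dispensing goes through it (Section 5.4). A subject given the wrong drug through an IXRS kit error was arguably dosed as the IXRS assigned, and the exception would then apply. This stands for that route only. It does not cover a site that hands over the wrong kit.

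**The clause is not wholly empty.** A reader might infer that the as-treated clause can never apply. The documents do not support that. Its wording also covers a wrong dosage or a wrong antiplatelet drug throughout, and such a subject may enter SAF and trigger it. It then defines no move to the other arm, but only the wrong-anticoagulant branch is unreachable.

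**The note need not contradict the grouping rule.** A reader might also infer that the entry rule, the exception and the note are three irreconcilable statements. The note can be read as concerning membership only, and two sets with the same members can be tabulated differently. On that reading the note does not conflict with as-treated grouping; it simply confirms who is left out.

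**The loss is limited.** It would go too far to say that these subjects disappear from all safety output. Bleeding is the primary endpoint and is analysed in ITT. Major bleeding, any bleeding, intracranial hemorrhage and the composite with all-cause death are also analysed in ITT. The listings of adverse events and abnormal laboratory values (Sections 11.5.1 and 11.5.2) are not expressly restricted to SAF.

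**The count may be zero.** First doses are supervised (Section 5.8), treatment is open-label, and INR and VKA dose are collected at least monthly in the VKA arm (Section 6.2.4). One corrected dose brings a subject into SAF. All of this stands and makes 15 subjects unlikely.

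**Conclusion.** The point holds for the wrong-anticoagulant case. As written, the SAF entry condition excludes a subject who took only the non-assigned anticoagulant, and the clause meant to regroup that subject cannot operate. The exclusion appears in both Section 11.1.4 and the synopsis, and the note confirms it.

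The consequence is small. It touches the SAF summaries only and leaves the non-inferiority and superiority tests and the secondary ITT analyses unchanged. The range of 3 to 15 subjects rests entirely on an assumed rate of 0.2% to 1%; nothing in the documents supports a particular rate.

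The conclusion assumes that IXRS assignment means the randomized anticoagulant. The protocol defers details to a SAP, and the text available contains no separate SAP section on this point, so a resolution there could not be checked. The protocol definition would still need correcting.

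**What to change.** - **Entry.** In Section 11.1.4 and the synopsis, define SAF as all randomized subjects with at least one dose of either study anticoagulant (edoxaban or VKA). Delete the qualifier on IXRS assignment in both places.
- **Grouping.** Keep the existing principle that subjects are analysed as randomized. The one exception is a subject who took only the other arm's anticoagulant during the entire study, who is grouped by the anticoagulant actually received. State that subjects who took both stay in their randomized arm. Grouping everyone by drug received, without this condition, would leave no rule for them.
- **Dosage.** Drop dosage from the regrouping clause, since a dose error does not change the arm.
- **Note.** Replace it with a statement that SAF may differ from mITT in membership and in grouping.
- **Treatment-emergent events.** In Section 11.5.1, tie the definition to study medication received rather than assigned, so that a restored subject has a clear start and end of the window. The reporting window in Section 9.4 has the same tie and should be aligned.

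The cost is a few lines of protocol text, plus matching lines in the SAP if it repeats the definition. Sample size, data collection at sites and the primary analysis do not change.
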